5. RANDOMISATION

5.1 Screening and Enrollment

Women who meet preliminary eligibility criteria: HIV uninfected and at substantial risk will be screened for further eligibility criteria following a signed screening informed consent. Blood will be drawn for haematology, liver function tests, blood chemistry tests, serology and HepB sAg assay.

Women who are confirmed eligible following screening will be requested to provide their informed consent for participation in the trial and thereafter enrolled in the study. Consent for specimen storage will also be sought. Enrolled participants will undergo a physical and pelvic examination accompanied by a genital specimen collection for storage. Blood will also be drawn for plasma, dried blood spot and cell pellet storage.

5.2 Randomisation

Following baseline clinical assessments, laboratory investigations and behavioural questionnaires, participants will be randomized to one of two arms (ARM A – Immediate PrEP or ARM B –Deferred PrEP) See Figure below. All participants will receive risk reduction counselling, STI screening and treatment, an invitation to the sexual partner to receive HCT and referral for treatment and support if he tests HIV positive and condom promotion. The randomisation method is described under the statistical section.

Randomisation – Treatment Arms

SOC – Standard of Care: Current recommendations for prevention and control of STIs in all pregnant women include:

- correct diagnosis by syndrome or laboratory diagnosis
- provision of effective treatment;

- reduction in or prevention of further risk-taking behaviour through age-appropriate education and counselling;
- promotion and provision of condoms, with clear messages for correct and consistent use; and
- notification and treatment of sexually transmitted infections in sexual partners, where applicable.

In the proposed study, we will screen for STIs using serological tests (syphilis, HSV-2) and genital tract screening using PCR molecular technology (chlamydia, gonorrhoea and trichomoniasis). Until laboratory results are received (approximately 1 week), pregnant women presenting with vaginal discharge or genital ulcers (symptomatic sexually transmitted infections) will be treated syndromically.

6.0 STUDY TREATMENT CONSIDERATIONS

The drug to be used in this study is Truvada (tenofovir disoproxil fumarate/ emtricitabine) which is the antiretroviral drug to be used to prevent HIV acquisition. TRUVADA tablets are fixed dose combination tablets containing emtricitabine and tenofovir disoproxil fumarate. EMTRIVA is the brand name for emtricitabine, a synthetic nucleoside analog of cytidine. Tenofovir disoproxil fumarate (tenofovir DF) is converted in vivo to tenofovir, an acyclic nucleoside phosphonate (nucleotide) analog of adenosine 5'-monophosphate. Both emtricitabine and tenofovir exhibit inhibitory activity against HIV-1 reverse transcriptase.

6.1 Study product formulation and storage conditions

Study Drug : Emtricitabine-Tenofovir disoproxil fumarate FTC-TDF Truvada[®] Formulation: 200 mg/300 mg tablets

Appearance: Blue, capsule shaped, film-coated tablet that are debossed with "GILEAD" on one side

Storage: 25°C (77°F) - Excursions permitted between 15-30°C (59-86°F). Keep container tightly closed. Each bottle contains thirty tablets with a silica gel desiccant canister that should remain in the original container to protect the product from humidity.

6.2 Treatment Procedures

- ARM A: Pregnant women allocated to ARM A will initiate Truvada on the day of randomization and will continue throughout peripartum until cessation of breastfeeding and thereafter given an option to continue PrEP until 18 months postdelivery.
- ARM B: Pregnant women allocated to ARM B will only initiate Truvada at cessation of breastfeeding and thereafter given an option to initiate PrEP until 18 months postdelivery.

6.3 Treatment Schedule

The treatment schedule is a once daily uninterrupted course.

6.4 Study product procurement

The study site pharmacist will order Truvada from the manufacturer (Gilead Sciences).

6.5 Study product accountability

The study pharmacist will maintain complete accountability and storage condition records of all study products received from Gilead Sciences and subsequently dispensed to study participants. All study products will be stored at the site study pharmacy. All unused study products will be returned to Gilead Sciences after the study is completed and terminated.

6.6 Study product dispensing

The site pharmacist will dispense a 28 day supply of tablets. The aim will be to provide the participant sufficient to last beyond the next scheduled visit. Dispensing of study product will be done either directly to the study participant or to authorized study staff if the participant is unable to present in person to the study pharmacy.

6.7 Study product returns

Participants must present with all remaining study product at each study visit conducted during the duration of the trial.

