7.7 Post-randomisation Procedures

All participants will receive support to the agreed plan to manage their personal risk and counselling about the importance of adhering to the agreed schedule of visits. A diary will be provided to record coital acts and condom use, different partners and pill taking when applicable.

For participants starting Truvada immediately, the clinician and participant will go through the instructions for use Truvada. They will be issued with 1 bottle, containing 30 tablets, and the next clinic appointment will be made for a four-week visit. They will be asked to tick the days they take the drug on the diary.

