7.9 Follow-up Visits until Delivery and Post-delivery

Following enrolment, women will follow the schedule of evaluations in Appendix 5. Women will remain on their assigned treatment arm until cessation of breastfeeding and thereafter follow their choice of either continuing or discontinuing ARV PrEP through the 18 month postpartum visit. Each participant will have follow-up visits approximately every four weeks (28 days) until delivery and following 72 hour postdelivery assessment the participant will be given an appointment for 2 weeks, 6, 10, 14 weeks and thereafter 4 weekly visits until week 74 (approximately 18 months post-delivery) at the study clinic.

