7.12 At Follow-up Visits during Product Use

At follow-up visits antenatal week 4 through week 74, study staff will:

- Update contact information (when necessary);
- Conduct pill count of product returned by participant, and document any product returned to participant;
- Collect information on adherence to the daily pill-taking regimen;
- Conduct risk reduction counseling, including pre- and post-test HIV counseling and distribute condoms;
- Conduct study product adherence counseling;
- Conduct contraceptive counseling as appropriate, re-supply contraceptive method as needed;

- Collect blood by venepuncture (10ml) and:
 - Perform HIV rapid antibody testing according to the algorithm described at the enrollment visit.
 - ✓ Test for ALT, AST, creatinine and phosphorus. If results are abnormal, repeat regularly until resolution to ≤ Grade 1 or until stabilization. Any required followup will be done per local standard of care.
 - ✓ Store plasma and ULPC aliquots for HIV PCR testing, QA and confirmatory laboratory testing as needed. Also store one plasma aliquot (if sufficient sample available) and one serum aliquot for potential future HIV related research;
 - ✓ Screen and treat other STIs using the syndromic management approach
 - Collect cervical/vaginal swabs for storage and subsequent screening for STIs using molecular techniques.
- Conduct adverse event assessment as per the US Division of AIDS Adverse Event Reporting and Toxicity Grading;
- Conduct physical and/or pelvic examination if clinically indicated; and
- Record medications taken since last visit.
- Complete the Final Status CRF if the participant does not require further follow-up due to risk of Hepatitis B flare and/or HIV seroconversion.

Participants will be allowed to complete each follow-up visit up to five days prior to and two (for the week 4 follow-up visit) or four (for later follow-up visits) days after their next 4-week (28 days) target visit date. If participants complete a visit outside the given window for that specific visit, the visit will be regarded an interim visit and an appointment for the next scheduled visit will be given.

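### Section 6.6 issues a 28-day supply for a 28-day visit interval, which leaves no reserve despite its stated aim and differs from the 30-tablet bottle in 7.7

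*Combined protocol and SAP*

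**What the plan says.** Section 6.6 sets the quantity: "The site pharmacist will dispense a 28 day supply of tablets". It then states the purpose: "The aim will be to provide the participant sufficient to last beyond the next scheduled visit". Section 6.3 requires daily dosing without interruption.

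Section 7.7, for women starting immediately, gives a different quantity for a four-week interval: "They will be issued with 1 bottle, containing 30 tablets, and the next clinic appointment will be made for a four-week visit". Section 6.1 confirms that a bottle holds thirty tablets and that the desiccant canister should stay in the original container.

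On timing, 7.9 says: "Each participant will have follow-up visits approximately every four weeks (28 days) until delivery". Section 7.12 lets a visit fall up to five days early, or late by "two (for the week 4 follow-up visit) or four (for later follow-up visits) days after their next 4-week (28 days) target visit date".

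On leftovers, 6.7 says: "Participants must present with all remaining study product at each study visit". Section 7.12 has staff count them and "document any product returned to participant". No section states a reserve that would reconcile 28 with 30.

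**The concern.** The quantity in 6.6 equals the visit interval. Read literally, a woman who takes every tablet arrives at an on-time visit with none left, and has days without drug if she comes late but within the permitted window. That misses the aim stated in the next sentence of 6.6. It also gives the pharmacy two quantities for one interval. Because 7.7 describes only the first issue to women starting immediately, later issues in Arm A, and all issues in Arm B, rest on 6.6.

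The stakes are modest. The women are selected for high HIV risk and the regimen is meant to be continuous. Adherence is also measured partly by pill count (6.9, 10.2), which needs a known number issued: a fully adherent woman attending on day 28 returns 0 tablets from 28, but 2 from 30.

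**Working it through.** The plan gives no figure for supply margin, so there is none to reproduce.

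**Inputs.** One tablet a day (6.3). Issue of 28 (6.6, read literally) or 30 (7.7). Target visits at day 28n (7.9). Latest permitted day 28 + 2 = 30 at week 4, and 28n + 4 afterwards (7.12). Convention: the first dose is taken on the day of issue, and the visit-day dose comes from the new supply.

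**Single interval, nothing carried over.** Tablets left = tablets issued − days to the next visit.

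- 28 tablets: 28 − 28 = 0 at an on-time visit; 28 − 32 = −4 at the +4 limit.
- 30 tablets: 30 − 28 = 2 on time; 30 − 30 = 0 at the +2 limit; 30 − 32 = −2 at the +4 limit.
- Covering the +4 limit without carry-over takes 32 tablets.

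**Arm A series.** Assume leftovers are kept, target dates are fixed from randomisation, and dispensing happens only at 4-weekly visits. The first issue is 30 (7.7). If later issues are 28, the tablets issued before visit n number 30 + 28(n − 1) = 28n + 2. Total uncovered days equal the largest value, over visits, of (visit day − tablets issued before it), or zero if none is positive. Six visits, each at its latest day:

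| Visit n | Latest day | Issued: 30, then 28 each | Day − issued | Issued: 30 each | Day − issued |
|---|---|---|---|---|---|
| 1 | 30 | 30 | 0 | 30 | 0 |
| 2 | 60 | 58 | 2 | 60 | 0 |
| 3 | 88 | 86 | 2 | 90 | −2 |
| 4 | 116 | 114 | 2 | 120 | −4 |
| 5 | 144 | 142 | 2 | 150 | −6 |
| 6 | 172 | 170 | 2 | 180 | −8 |

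With 30 and then 28, the worst total is 2 days: 2/172 = 1.2%. It does not grow after the second visit, because 28n + 4 − (28n + 2) = 2 for every later n. The week-4 window is fully covered. With 30 at every visit, the worst total is 0.

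**If the 2-week antenatal visit in Appendix 5 also dispenses.** A further 28 tablets gives 28n + 30 before 4-weekly visit n, which exceeds 28n + 4, so the gap is 0. The documents do not say whether that visit dispenses.

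**Woman starting at a later visit (Arm B after breastfeeding cessation).** She has nothing carried over. If 28 tablets are issued on a target date and the next visit is at +4, she is 32 − 28 = 4 days short. With 30 she is 32 − 30 = 2 days short. With two bottles she has 60 − 32 = 28 left. A first issue made late in its own window shortens the interval and so reduces the gap.

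**The case against.** The best defence is that a 28-day supply is not a tablet count. Section 6.6 itself says the supply should outlast the visit, bottles hold thirty, the canister should stay in the original container, and 7.7 issues one bottle for four weeks. Read together, these suggest one bottle per visit, and nothing tells the pharmacist to open a bottle and remove two tablets. The 2-day allowance at week 4 also matches a 30-tablet bottle exactly. Other provisions soften a gap: product may be dispensed "to authorized study staff if the participant is unable to present in person to the study pharmacy", and 7.17 prompts a telephone reminder after a missed visit.

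Most of this stands, and it makes an actual shortfall unlikely. It does not remove the discrepancy. If full bottles are the practice, 6.6 misdescribes it, although 6.5 requires complete accountability for what is dispensed.

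A reader might infer more than the documents support. Applying 28 tablets from the first issue would give 4 uncovered days of 172 (2.3%), but 7.7 sets Arm A's first issue at 30, so that figure is wrong for Arm A. A reader might also picture the gap persisting through one long unbroken 4-weekly series. Delivery breaks the series with visits within 72 hours and at 2 weeks (7.9, 7.11). Finally, simply aligning 6.6 with 7.7 might seem enough. It is enough only with carry-over, fixed target dates and a start at randomisation.

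**Conclusion.** The point holds as a minor inconsistency. Read literally, 6.6 leaves no reserve at an on-time visit, contrary to its own aim, and it differs from 7.7 by two tablets per issue.

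For Arm A the worst case is 2 uncovered days in an antenatal series (about 1.2% of 172 days). This assumes 28-tablet later issues, full adherence, leftovers kept, fixed targets, visits as late as permitted and no dispensing at the 2-week visit. For a woman first issued 28 tablets at a later visit, the worst case is 4 days, provided that issue is on its target date and the +4 allowance applies to her next visit.

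It would be tempting to read this as a threat to the safety comparison, since missed doses reduce exposure. The size does not support that: the gap is a few days at most, arises only on a literal reading, and bears on no sample size, power or significance level. No effect on the non-inferiority comparison is claimed.

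**What to change.** In 6.6, replace the 28-day supply with one original 30-tablet bottle per 4-weekly visit, matching 7.7. Add three short statements:

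- Leftover tablets are handed back after the pill count, as 7.12 already envisages.
- Visit target dates stay fixed and are not reset from the last attendance.
- Women whose first issue is at a later visit, chiefly Arm B after breastfeeding cessation, receive a second bottle at that issue, because 30 tablets without carry-over do not reach the +4 limit.

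The cost is a sentence or two in 6.6, a pharmacy instruction, two more tablets per issue than 28, and one extra bottle per later starter. No extra visits or participants are needed.

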6.8 Adherence counselling

Adherence counselling will be provided to study participants upon enrolment and additionally at specified intervals. Counselling will address topics such as participantcentred strategies to remember to take the tablets every day, to ensure the availability of the tablets both in the home and away from home; and to identify and discuss various challenges and situations that may impede daily tablet adherence.

6.9 Adherence assessment

Data on adherence to the daily regimen of TDF/FTC will be collected at each study visit via pilot tested interview tools and pill count. Additionally, stored plasma specimens collected during the trial at each scheduled visit from suspected HIV seroconvertors will be archived for analysis of markers of product adherence to enhance interpretation of the results of the study.

6.10 Concomitant, prohibited, and precautionary medications

The following medications are not permitted:

- Drugs containing emtricitabine or tenofovir disoproxil fumarate
- Adefovir dipoxil
- Lamivudine and other cytidine analogues
- Didanosine
- Cidofovir and other medicinal products that compete for active tubular secretion
- Drugs that reduce renal function

6.11 Treatment after HIV Seroconversion

Participants who seroconvert during pregnancy or during breastfeeding will stop Truvada and will be managed according to national guidelines. Women will receive the fixed dose combination of TDF/FTC/EFV as per national guidelines. The participant will be monitored for treatment response and drug resistance. They will continue in follow-up until end of study.

If daily Truvada is required to treat active replication of hepatitis B acquired after enrolment, that will take precedence over the randomization allocation. Participants will continue in follow-up until end of study.

6.12 HIV Prevention Post Breastfeeding Cessation

Participants in both arms will be offered PrEP post breastfeeding cessation until end of study at 18 months after the last participant enrolled has delivered. Thereafter, participants who remain at high risk will be referred to the nearest Dreams PrEP Demonstration site or the National PrEP Program site whichever is available at the time of study completion. The study is expected to be complete by June 2019. We believe that there would be at a minimum ONE PHC or NGO that will be a PrEP service delivery site in Umlazi by the time of study completion. PrEP is slated to be included in the PEPFAR-supported DREAMS initiative focused on young women and adolescent girls. PrEP is also included in the National Strategic Plan (NSP) for HIV, STIs and TB (2012-2016).

7.0 ASSESSMENTS AND FOLLOWUP PROCEDURES

7.1 Source of Study Population

HIV uninfected pregnant women attending any of the three busiest clinics in Umlazi (D, H and U Clinics) will be informed of the study. Interested volunteers will be transported to the Umlazi Research Clinic for screening. Distance between PHC clinics and the Research Clinic is approximately 5 to 10 km.

7.2 Cohort Accrual and Follow-up

Cohort accrual is expected to be completed in 12 months. Accrual to this study will be monitored by the Protocol Team in accordance with standard operating procedures. An overview of the study procedures for women and their infants are provided in Appendices 5 and 6. The women will follow the basic antenatal care schedule. For participants with early antenatal booking (<12 weeks), return visits will be scheduled for 20, 26-28, 32-34, and 38 weeks until delivery. Following delivery and a <72 hour postdelivery assessment women and their infants will be seen at 6, 10, 14 weeks and thereafter 4 weekly until 18 months postdelivery.

7.3 Pre-screening

Pregnant women attending antenatal clinics at off-site locations in Umlazi will be prescreened by study staff to ascertain preliminary eligibility. These criteria include:

- 18<24 years
- No major obstetric complications
- Women plan to reside in the area for the next 2 years
- Tested HIV negative at the off-site location

During these interactions, the study staff will explain the study to the potential candidates for study participation. Process information (e.g. number of potential participants contacted, number potentially eligible, number interested in further screening) will be recorded and stored at the Research Site. Participant information will not be linked to participant identifiers.

7.4 Screening

Screening and enrolment procedures will be completed within 14 days. Eligibility will be determined using a combination of biomedical and behavioural criteria. If a participant is not enrolled within 14 days of providing informed consent for screening, the participant will not be re-screened or enrolled. Screening will be completed in a step-wise manner. Firstly, potential participants will be invited to screen for the study and asked to provide informed consent for screening (Appendix 1). Potential study participants will be assigned a screening number, followed with a risk assessment (Appendix 2) and the first series of biomedical screening procedures including confirmation of HIV uninfected status. If both HIV test results are negative, the potential participant will be invited to continue with the screening process and will be asked to provide demographic information, locator information and blood for chemistry and haematological tests.

HIV Prevention Pregnancy Post-delivery Version 1.0

7.5 Enrolment

At screening, eligible participants will have been given a date to return to the clinic for enrollment. This date will be within two weeks of screening. If a participant does not return within 14 days of the screening visit, she will not be enrolled nor re-screened. At the enrollment visit, if the participant meets all eligibility criteria that can be known from the screening visit, study staff will obtain informed consent for study participation (Appendix 3). Informed consent will also be obtained for blood to be stored for future HIV related research (Appendix 4). A participant may refuse this procedure and still be part of the study. All study procedures listed in the Schedule of Evaluations for the mother (Appendix 5) and for the HIV unexposed infant (Appendix 6) will follow.

There will be a clinic interview, during which baseline demographic, clinical and behavioural data will be collected on a case record form. The behavioural and lifestyle information provided by the individual together with results from the screening for sexually transmitted infections will inform the development of a personalised plan for reducing their risk. A personalised invite to the sexual partner will be provided to all participants. The invitation is intended to encourage partners to test for HIV and be referred for ART if HIV positive. Partners will also be informed of their options for HIV prevention and what is available in the public sector.

Participants will receive supplies of condoms in quantities anticipated to last until the next visit. A participant can return between scheduled visits to obtain more condoms.

7.6 Randomisation Procedures

Randomisation will be performed on the day of the enrolment visit after the eligibility checklist is confirmed. Randomisation will be performed using a computer-generated randomization list. The participant's study number, allocation and the date of randomization will be entered into the Trial Register at the Research Site.

7.7 Post-randomisation Procedures

All participants will receive support to the agreed plan to manage their personal risk and counselling about the importance of adhering to the agreed schedule of visits. A diary will be provided to record coital acts and condom use, different partners and pill taking when applicable.

For participants starting Truvada immediately, the clinician and participant will go through the instructions for use Truvada. They will be issued with 1 bottle, containing 30 tablets, and the next clinic appointment will be made for a four-week visit. They will be asked to tick the days they take the drug on the diary.

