7.21 Procedures for Assessing Safety

Participants will be asked one month after starting Truvada and at each subsequent scheduled visit whether they have had any admissions to hospital, or suffered from any significant illness that required medical attention. The site clinician will determine whether an illness meets the criteria for Serious Adverse Event (SAE) Reporting. SAEs will be reported to the UKZN BREC, Medicines Control Council and Department of Health. Participants will also be asked whether they have experienced any side effects.

Clinical assessments during pregnancy will be conducted as per the national guidelines for maternity care.

Maternal safety assessments during pregnancy and until 74 weeks study exit: All women will have bloods drawn for chemistry and haematological investigations at screening, enrolment, 2 weeks, 4 weekly until delivery, <72 hours of delivery, 2 weeks post delivery, 6 weeks, 10 weeks, 14 weeks and 4 weekly until 74 weeks (inclusive). Chemistry tests include liver function markers (ALT/AST/Phosporous), renal function (serum creatinine/urea/sodium/potassium), and bone density markers (serum calcium and magnesium).

Bone mineral content in the mother will be measured by DXA scan at 6 weeks postpartum, 6 months, 12 months and 18 months. Both Hip and Spine DXA scans will be done at above scheduled visits.

Within 72 hours of delivery, the participant with her maternity care record (MCR) will be reviewed by the study clinician. Fetal outcome in addition to other obstetric data will be extracted from the MCR. The following definitions will be used to document fetal outcome:

NON-VIABLE FETUS (MISCARRIAGE)

Less than 28 weeks* gestation and where there is no evidence of life at delivery. **STILL BIRTH** Gestational age of 28 weeks or more and where there is no evidence of life at delivery. **NEONATAL DEATH**** Death after a live birth whatever the duration of the pregnancy. **When the gestational age is not known, a legal weight cut-off of 1000 g is used.**

Maternal gestational age will be determined by clinical and obstetric assessments that will include an Ultrasound, measurement of symphysis fundal height and last menstrual date if known. Preterm delivery is defined as < 37 weeks. Moderate preterm delivery 32-35 weeks and severe preterm delivery <32 weeks.

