APPENDIX 5 SCHEDULE OF EVENTS FOR MOTHER

		ANTENATAL			LABOUR AND DELIVERY	POSTNATAL					
	SCREENING 1 ^{sr} ANTENATAL VISIT	2 [№] ANTENATAL ENROLMENT 14W	3 RD ANTENATAL 2 WEEKS	SUBSEQUENT 4 WEEKLY ANTENATAL	<72 HOURS POST DELIVERY	2 WEEKS	6 WEEKS	10 WEEKS	14 WEEKS	SUBSEQUENT 4 WEEKLY POSTNATAL	74 WEEKS/STUDY EXIT
Study Informed Consent	Х	Х									
Storage Informed Consent		х									
Documented HIV test result	Х	~									
HIV Risk Assessment	Х										
Medical History	Х										
Hx, Signs/Sx of STIs	Х		Х	Х	Х	Х	Х	Х	Х	Х	Х
Pregnancy Ultrasound	Х										
Obstetric Assessments	Х	Х	Х	Х							
DXA Scan Hip and Lumbar Spine							Х			X*	Х
Physical Exam	Х	Х	Х	Х	Х	Х	Х	Х	Х	Х	Х
Randomisation		Х									
Sexual Behaviour Questionnaire	Х	Х	Х	Х	Х	Х	Х	Х	Х	Х	Х
Drug Adherence Interview			Х	Х	Х	Х	Х	Х	Х	Х	Х
Condom Usage Interview		Х	Х	Х	Х	Х	Х	Х	Х	Х	Х
Risk Reduction Counselling		Х	Х	Х	Х	Х	Х	Х	Х	Х	Х
Laboratory Investigations											
RPR Test	2ml								2mL		2mL
HIV Rapid Test (finger prick)	Х	Х	Х	Х	Х	Х	Х	Х	Х	Х	Х
Hep B Surface Antigen	2ml						2mL				2ml
ALT/AST/Phosporous		2ml		2mlª				2ml		2mlª	
CBC	2ml		2ml	2mlª	2mL				2mL	2mlª	
Serum Creatinine	2mL		2mL	2mL		2mL		2mL	2mL	2mL	2mL
Stored EDTA Plasma, DBS /cell pellets		10mL	10mL	10mL	10mL	10mL	10mL	10mL	10mL	10mL	10mL
Stored Breast Milk (during BF only)						10mL	10mL	10mL	10mL	10mL	10mL
Cervical Vaginal Swabs		Х	Х	Х			Х	Х	Х	Х	Х
TOTAL BLOOD VOLUME	8ml	12ml	14ml	16ml	12ml	12ml	12ml	14ml	14ml	16ml	12ml

* DXA scan at 6 and 12 months

APPENDIX 6

SCHEDULE OF EVENTS FOR HIV UNEXPOSED INFANTS

	BIRTH	6 WEEKS	26 WEEKS	50 WEEKS	72 WEEK/STUDY EXIT VISIT
Physical Exam	Х	Х	Х	Х	Х
Growth Parameters and neurodevelopmental milestones	Х	X	Х	Х	X
DXA Scan Lumbar Spine and Whole Body		Х	Х	Х	X
Laboratory Investigations					
CBC	2mL	2ml	2mL	2mL	2mL
Serum Creatinine	2mL	2ml	2mL	2mL	2mL
Stored DBS	Х	Х	Х	Х	Х
TOTAL BLOOD VOLUME	4ml	4ml	4ml	4ml	4ml

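### Section 7.7 books women starting Truvada for four weeks, which contradicts the 2-week visit and bloods in Section 7.21 and Appendix 5

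*Combined protocol and SAP*

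**What the plan says.** Section 7.7 covers women who begin Truvada straight after randomisation, that is, Arm A. They receive one bottle of 30 tablets, and "the next clinic appointment will be made for a four-week visit".

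Section 7.21 sets the maternal safety bloods without distinction by arm: "All women will have bloods drawn for chemistry and haematological investigations at screening, enrolment, 2 weeks, 4 weekly until delivery". The chemistry it lists is liver markers with phosphorus, creatinine with urea and electrolytes, and calcium with magnesium. Its questions on illness and side effects start later: "Participants will be asked one month after starting Truvada and at each subsequent scheduled visit".

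Appendix 5 has a column headed "ANTENATAL 2 WEEKS" between the enrolment and randomisation column and the 4-weekly antenatal visits. It is not split by arm. It carries a blood count, creatinine, an HIV rapid test, a drug adherence interview and stored blood.

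Section 7.9 begins by deferring to the appendix: "Following enrolment, women will follow the schedule of evaluations in Appendix 5". It then gives its own summary: "Each participant will have follow-up visits approximately every four weeks (28 days) until delivery". Section 7.5 also says that the Appendix 5 procedures follow enrolment. Section 7.8 describes an assessment after one month on drug, with creatinine. No section says which text prevails if they differ.

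**The concern.** Section 7.7 is the instruction that staff would use on randomisation day to make the booking. Taken literally, it leaves no room for a visit at 2 weeks.

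That visit is the first laboratory check after a pregnant woman starts the drug. Creatinine clearance is among the main outcomes in Section 10.2. Section 1.10 reports that six participants in the TDF-containing arms of the discordant-couples PrEP trial discontinued for raised creatinine, against none on placebo. What is at stake is one early safety check in Arm A: a transient change that resolves before week 4 could go unseen.

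**Working it through.** **1. Is the 2-week column real, or damage to the table?** Adding the blood volumes in Appendix 5 down each column gives:

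- Screening: RPR 2 + hepatitis B antigen 2 + blood count 2 + creatinine 2 = 8 ml (stated 8 ml).
- Enrolment: ALT/AST/phosphorus 2 + stored 10 = 12 ml (stated 12 ml).
- Antenatal 2 weeks: blood count 2 + creatinine 2 + stored 10 = 14 ml (stated 14 ml).
- Antenatal 4-weekly: ALT/AST/phosphorus 2 + blood count 2 + creatinine 2 + stored 10 = 16 ml (stated 16 ml).

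All four totals match. The blood count and creatinine therefore belong to the 2-week visit, and ALT/AST/phosphorus does not. Section 7.21 names the same time point independently, so the visit is planned in two places.

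**2. The instructions for an Arm A woman, side by side.**

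| Source | First contact after randomisation |
|---|---|
| 7.7 | four weeks |
| 7.21 (bloods) | 2 weeks |
| Appendix 5 | 2 weeks |
| 7.9 | Appendix 5 by reference, then about every 28 days |

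Only 7.7 excludes the 2-week visit. Section 7.9 leaves it out of its summary but points to the schedule that contains it.

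**3. The delay if 7.7 is followed.** Week 4 minus week 2 is 28 − 14 = 14 days. The documents give the 2-week visit no target day and no window, so any range rests on an assumption. Section 7.12 allows the week-4 visit from 5 days before to 2 days after its target, that is, from day 28 − 5 = 23 to day 28 + 2 = 30. If the 2-week visit fell exactly on day 14, the delay would be 23 − 14 = 9 to 30 − 14 = 16 days. If Appendix 5 is followed, the delay is zero.

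**4. What would be skipped.** Of the 14 ml, the safety tests take 2 + 2 = 4 ml, and the other 10 ml is stored blood. The HIV rapid test and adherence interview at that visit would also be missed. Appendix 5 shows creatinine at screening, none at enrolment, and then at 2 weeks, so this is its first creatinine after randomisation.

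**5. Who is affected.** The 7.7 instruction applies only to women starting Truvada immediately. It gives no such booking for Arm B.

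**6. A second mismatch at the same visit.** Section 7.21 asks for its full chemistry panel at 2 weeks. Appendix 5 lists only creatinine and the blood count, as the 14 ml total in step 1 confirms.

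**The case against.** The strongest reply is that the protocol already settles the matter. Sections 7.5 and 7.9 send staff to Appendix 5, Section 7.2 cites it as the overview, and nothing points to 7.7 as the visit schedule. The 7.7 sentence follows the issue of a 30-tablet bottle and leads into the one-month assessment in 7.8, so it can be read as the resupply appointment. The consequence is also small: women with a creatinine clearance below 70 mL/min are excluded at screening, and creatinine is repeated at one month.

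Most of this stands. It makes a missed visit less likely and limits the effect if one is missed. It does not remove the contradiction, because 7.7 speaks of the next clinic appointment, not of resupply, and there is no precedence rule.

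Four stronger readings may tempt a reader, and the documents do not support them:

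- *That 7.2, 7.9 and 7.12 contradict the visit too.* The dates in 7.2, "return visits will be scheduled for 20, 26-28, 32-34, and 38 weeks until delivery", may describe routine antenatal care. Section 7.9 defers to Appendix 5. Section 7.12 lists procedures from antenatal week 4 and does not say that no earlier visit occurs.
- *That the delay runs from 5 to 21 days.* This applies to the 2-week visit a window that 7.12 gives to visits after week 4.
- *That early safety data are biased between arms.* Sampling could differ by arm if 7.7 is followed, but nothing shows that it would, or that a comparison would be distorted.
- *That the safety questions in 7.21 must also move to 2 weeks.* That would be a preference, and the conflict can be resolved without it.

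**Conclusion.** Minor, and wrong as written. Section 7.7 contradicts Section 7.21 and Appendix 5 on the first visit after Truvada is started.

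The size is conditional. If 7.7 is followed, the first on-drug creatinine and blood count in Arm A come a nominal 14 days late, and one planned check is skipped. This takes the 2-week visit as day 14 and the next as day 28. It also takes the day-28 blood count from the 4-weekly bloods in 7.21 and Appendix 5, because 7.8 names creatinine but not a blood count. If Appendix 5 is followed, nothing is lost.

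A persistent renal change would still be seen at one month. The sample size rests on preterm delivery and is unaffected.

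**What to change.** - **7.7:** state that the next appointment is the 2-week visit in Appendix 5, followed by the four-week visit.
- **7.9:** name the 2-week antenatal visit for both arms, with a day-14 target, a window, and tests as listed in Appendix 5.
- **7.21 and Appendix 5:** align the 2-week tests. Either limit 7.21 at that visit to creatinine and the blood count, or add the wider panel to the Appendix 5 column.

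The 7.12 list should not simply be extended to this visit. It includes ALT, AST and phosphorus, which Appendix 5 does not schedule at 2 weeks.

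The cost is a few sentences. No visit is added to Appendix 5, and the 30 tablets issued at randomisation already last past day 14, so dispensing does not change. No test is added to Appendix 5 if its list is kept. If the 7.21 panel is preferred, ALT/AST/phosphorus alone would add the 2 ml that Appendix 5 allots to it elsewhere, giving 14 + 2 = 16 ml. The documents give no volume for the remaining analytes.
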